- Anticipated enrollment was modified from 600 participants to 400 participants to reflect current enrollment trends and expected study sample size

¹ Note that several details related to study implementation described in the September 2017 Evaluation Abstract have changed over the course of the study, but for the purposes of transparency and documentation we have included the original abstract in Appendix B.

1) Research Questions that Address Program Effectiveness on Behavioral Outcomes

a. Primary research questions

1. What is the impact of the offer to participate in *Practice Self-Regulation* (treatment) relative to the offer to participate in typical therapy or counseling (control) on participants' reported number of sexual partners nine months after receiving the treatment?
2. What is the impact of the offer to participate in *Practice Self-Regulation* (treatment) relative to the offer to participate in typical therapy or counseling (control) on participants' reported number of times having sex without a condom nine months after receiving the treatment?

b. Exploratory research questions

Exploratory research questions will investigate mediating factors, subgroup effects, outcomes immediately post therapy, and other behavioral outcomes.

2) Description of the Intervention and Counterfactual Condition

The Teen Health Study (THS) is a randomized controlled trial (RCT) in which eligible, consenting participants are randomly assigned to a treatment or control intervention at partnering outpatient mental health agencies, clinics, or private practitioners' offices located in five states – California, Louisiana, Maine, Michigan, and New Mexico.

The intervention is offered to youth, aged 14 to 19, who are receiving outpatient counseling services from a master's-level trained therapist at one of the study's implementation sites, have been deemed appropriate for the study by clinic staff with regards to physical and mental health capacity, have not previously used the *Trauma Outcome Process* (TOP) workbook in therapy, do not live with any youth who are enrolled in the Teen Health Study, have not participated in other Office of Adolescent Health-funded Teen Pregnancy Prevention (OAH TPP) programs, consent to participate in the study, and are willing to complete post-program and nine-month follow-up questionnaires.

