3. Determine if logical imputations are possible for any analytic variables that may have missing values (due to nonresponse) and logically impute where this is the case. We will not logically impute where the missing values are previously inconsistent, unreliable, or invalid.
4. Determine if any individuals who are in the randomized sample (for each outcome) do not have outcome data at the nine-month follow-up time point. If this is the case, our proposed benchmark approach is to use case deletion, as we feel it is the most straightforward and prudent approach for missing follow-up data

²⁶ Puma, M.J., Olsen, R.B., Bell, S.H., Price, C. (2009). What to Do When Data Are Missing in Group Randomized Controlled Trials. (NCEE 2009-0049). Washington, DC: National Center for Education Evaluation and Regional Assistance, Institute of Education Sciences, U.S. Department of Education. Moher, D. et al. (2010). CONSORT 2010 Explanation and Elaboration: Updated Guidelines for Reporting Parallel Group Randomised Trials. *BMJ* 2010;340:c869.

²⁷ We will code missing responses with a unique missing code that identifies or flags these missing values according to the reason they are missing (i.e., nonresponse, invalid, inconsistent). Unreliable data are not recoded to missing, rather cases deemed unreliable are coded as 1 in an indicator variable, treated as unit missing, and excluded from analysis. See the *Data cleaning* section or Table 3 in the Appendix for details on how missing data are coded.

²⁸ For item missing values, we will only report prevalence of missing and inconsistent data for variables that are included in our model specifications and could therefore influence the constitution of the analytic sample.

recommended in Puma et al. (2009). These cases will be deleted from the analytic sample and attrition statistics will be reported.

5. Determine if any individuals who are in the randomized sample (for each outcome) are missing baseline covariates or the baseline measure of the outcome variable. If this is the case, our proposed benchmark approach is to use dummy variable adjustment procedures, as we feel it is the most straightforward and prudent approach for missing baseline/covariate data recommended in Puma et al. (2009).

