Y_{Post} – The outcome variable of interest, either: 1) times having sex without condoms in the past 3 months (continuous; values range 0 to k , where 0= has had sex without condoms 0 times in past 3 months, and k = number of times having sex without condoms in past 3 months); or 2) number of sexual partners in the past 3 months (continuous; values range 0 to k , where 0= has 0 sexual partners in past 3 months, and k = number of sexual partners in past 3 months) reported by participant i at the 9-month follow-up. (see Table 1 for full details on the variable construction).

Y_{Pre} – The baseline measure of the outcome variable of interest reported by participant i at baseline (see Table 2 for full details on the variable construction); variable will be re-centered at the grand mean for analysis.

³⁹ With the assumption that we maintain low attrition and differential attrition and that the study otherwise executes the RCT with integrity, we should be able to estimate an un-biased estimate of the average treatment effect of the intent to treat participants with *PS-R* by comparing differences in the means of the outcome variable reported by the treatment group with those reported by the control group. We could then provide a compelling response to our research question by testing the hypothesis that there is no difference between the two groups using straight-forward hypothesis testing statistics (t-test). With that said, we propose a regression-based model that includes covariates, because randomization should ensure covariates are uncorrelated with the treatment variable (i.e., they should not affect the estimate of the treatment effect), and in the instance they are significant predictors of the outcome, their inclusion in a regression model will decrease the standard error of the estimates, making them more precise. See: Angrist, J. D., & Pischke, J. (2009). Mostly harmless econometrics: An empiricist's companion. Princeton: Princeton University Press; Rosenblum, M. and van der Laan, M. J. (2009), Using Regression Models to Analyze Randomized Trials: Asymptotically Valid Hypothesis Tests Despite Incorrectly Specified Models. *Biometrics*, 65: 937-945. doi:10.1111/j.1541-0420.2008.01177.x.

⁴⁰ As part of our sensitivity analyses, we will construct a logistic regression model to explore any potential differences in our effect estimates given the model utilized.

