β_1 – This is the parameter estimate of substantive interest. β_1 represents, depending on the outcome measure of interest in the analysis, either: 1) the adjusted mean difference in treatment and control participants' self-reported times having sex without condoms in the past three months at the nine-month follow-up; or 2) the adjusted mean difference in treatment and control participants' self-reported number of sexual partners in the past three months at the nine-month follow-up.

ε – The error term or unexplained individual-level variance that remains for each observation after the structural components of the model are estimated. It is the difference between the observed and the predicted values at the individual level.

We will report model-estimated effects and the results of significance tests in the findings section of the final impact report. Statistical significance will be based on test statistics produced by Stata for the coefficient β_1 using a two-tailed test, with $p < .05$.

- ii.* **Sample attrition:** Overall and differential attrition will be calculated using the full sample of participants enrolled in the study. This will be determined using data within the *Participant Database*. We will calculate overall attrition using the following formula:

$$Attrition_{participant} = 1 - \left(\frac{Assessed_{participant}}{Base_{participant}} \right)$$

where:

$Attrition_{participant}$ - the proportion of participants enrolled in the study who did not complete a 9-month follow-up questionnaire
 $Base_{participant}$ - the number of participants enrolled into the study
 $Assessed_{participant}$ - the number of participants who completed a 9-month follow-up questionnaire

Differential attrition will be calculated using the following formulas:

$$Attrition_{participant} C = 1 - \left(\frac{Assessed_{participant} C}{Base_{participant} C} \right)$$

$$Attrition_{participant} T = 1 - \left(\frac{Assessed_{participant} T}{Base_{participant} T} \right)$$

$$Differential\ Attrition_{t-c} = abs(Attrition_{participant} T - Attrition_{participant} C)$$

Where:

$Differential\ Attrition_{t-c}$ - the absolute difference between the proportion of treatment group participants who did not complete a 9-month follow-up questionnaire and the proportion of control group participants who did not complete a 9-month follow-up questionnaire

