2. Beginning with the largest p-value (p_{k1}), we will assess if $p_{k1} < ((i/m)a^*)$, where $m =$ the total number of tests conducted, and a^* = the initial significance value at which we would reject the null hypothesis and the level of false discovery we are willing to accept (in this case, 0.05). The null hypothesis will be rejected and the test will be considered statistically significant if $p_{k1} < ((i/m)a^*)$. If $p_{k1} < ((i/m)a^*)$, all smaller p-values in the list will also be considered statistically significant and the null hypothesis will be rejected for each test. If $p_{k1} \geq ((i/m)a^*)$, the null hypothesis will hold, the test will not be considered statistically significant, and the next largest p-value in the ranked list will be assessed.
3. If the 1st p-value is not statistically significant, the 2nd largest p-value in the list (p_{k2}) will be compared against $(i/m)a^*$. The null hypothesis will be rejected and the test will be considered statistically significant if $p_{k2} < ((i/m)a^*)$. If $p_{k2} < ((i/m)a^*)$, all smaller p-values in the list will also be considered statistically significant and the null hypothesis will be rejected for each test. If $p_{k2} \geq ((i/m)a^*)$, the null hypothesis will hold, the test will not be considered statistically significant, and the next largest p-value in the ranked list will be assessed.
4. If the 2nd p-value is not statistically significant, the 3rd largest p-value in the list (p_{k3}) will be compared against $(i/m)a^*$. The null hypothesis will be rejected and the test will be considered statistically significant if $p_{k3} < ((i/m)a^*)$. If $p_{k3} \geq ((i/m)a^*)$, the null hypothesis will hold and the test will not be considered statistically significant.

iii. **Sensitivity analyses:** We will conduct sensitivity analyses to test the robustness and validity of our benchmark approaches outlined above. These include: (1) excluding covariates; (2) not adjusting for missing baseline data; (3) excluding unreliable data; (4) excluding outliers; (5) condensing data collection windows to exclude late responders; and (6) estimating an empirical model that uses appropriate alternative approach if analytic sample size is not sufficient for benchmark approach.

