5. **Condensed data collection windows.** Our benchmark approach is to include follow-up data from all participants who completed a questionnaire during their open data collection window, regardless of the time point in that window when it was completed. Data collection windows are broad to minimize attrition from the analytic sample. To examine whether or not this influences our results – and, in particular, whether or not study participants who respond later report different outcomes from those who respond earlier – we will conduct an analysis that examines the difference, if any, in response time between treatment and control participants and compares impact estimates for analytic samples without late responders. Late responders will be defined as those participants who complete their nine-month questionnaire more than one month after the initiation of the nine-month data collection window.
6. **Using alternate model specification.** Our benchmark approach is to use OLS regression to estimate the effects of the intervention on each of our primary outcomes of interest. This approach is deemed appropriate even in the instance the dependent variable is not normally distributed – as may be the case with our outcomes – so long as the sample size is sufficiently large.⁴³ In the instance our analytic sample size does not reach 500 participants (the threshold at which we consider a sample large), we propose to conduct diagnostic tests to identify an appropriate alternative estimation approach (e.g., transformation of the dependent variable, Bayesian approach, non-parametric model) that will be used to conduct sensitivity analyses to test the robustness of our results.

5. **Additional planned analyses:** We intend to investigate the following exploratory research questions in addition to the primary research questions described above.

Antecedents of Sexual Behavior

- a. What are the short-term (post-program) and long-term (nine-month follow-up) impacts of the offer to participate in *PS-R* (treatment) relative to the offer to participate in *TPG* (comparison) on the following antecedents of participants' sexual behavior:
 - i. Perception of risk and severity for pregnancy and HIV/STIs

⁴³ Lumley, T., Diehr, P., Emerson, S., Chen, L. (2002). The Importance of the Normality Assumption in Large Public Health Datasets. *Annual Review of Public Health*. 23:151–69
DOI: 10.1146/annurev.publhealth.23.100901.140546

- ii. Intention to have sex

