Sample enrollment and baseline data collection began July 2016 and will end December 2018. The 18-week post-baseline data collection began November 2016 and will end September 2019, and the 9-month follow-up data collection began August 2017 and will end June 2020.

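### Does the check on OLS below 500 participants, certain to run at 400 expected, have to name a method that keeps the mean difference?

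*Combined protocol and SAP*

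**What the plan says.** Section 4)f.i estimates program effects on both primary outcomes by OLS. Its coefficient β₁ is defined as "the adjusted mean difference in treatment and control participants" on the count scale, tested two-sided at 0.05. Section 4)f then applies Benjamini-Hochberg across the primary outcomes. Section 4)a ties a positive finding to fewer reported events under PS-R together with a significant group difference.

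Item 6 of the sensitivity analyses accepts OLS for non-normal outcomes when the sample is large, and then sets the limit: "In the instance our analytic sample size does not reach 500 participants (the threshold at which we consider a sample large". Below it, diagnostic tests are to identify an alternative, with examples given as "transformation of the dependent variable, Bayesian approach, non-parametric model) that will be used to conduct sensitivity analyses". The list that opens the sensitivity section describes the same step as "estimating an empirical model that uses appropriate alternative approach if analytic sample size is not sufficient for benchmark approach".

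Footnote 40 separately states that "we will construct a logistic regression model to explore any potential differences in our effect estimates given the model utilized". It gives no binary outcome and no cut-point, and the opening list does not mention it.

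On sample size, the study changes timeline for November 2018 records: "Anticipated enrollment was modified from 600 participants to 400 participants to reflect current enrollment trends and expected study sample size". For missing follow-up, section 4)c.v step 4 says "our proposed benchmark approach is to use case deletion".

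**The concern.** The plan appears to defeat its own justification. It rests OLS on a sample of 500, expects 400, and describes a smaller sample as not sufficient for the benchmark. A step written as a contingency is in effect a planned analysis with no named method.

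The check may also miss its target. β₁ is a difference in mean counts. A transformed outcome gives an effect on another scale, a rank-based model tests a shift in the whole distribution, and a logistic model asks whether any event occurred. Each can disagree with β₁ when nothing is wrong with OLS. If the report read such disagreement as lack of robustness, a true effect could be presented as fragile, and that reading would depend on which listed option was picked.

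**Working it through.** **1. Does the check run?** Inputs are 400 expected (study changes timeline), 500 as the limit (item 6) and deletion of cases without outcomes (section 4)c.v). The plan gives no attrition rate, so *d* is assumed.

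Analysed N = 400 × (1 − *d*):
- *d* = 0: 400
- *d* = 15%: 400 × 0.85 = 340
- *d* = 25%: 400 × 0.75 = 300
- *d* = 30%: 400 × 0.70 = 280

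Reaching 500 would need 500 / 400 = 125% follow-up. At the former target of 600, the limit could have been met with attrition up to 1 − 500/600 = 16.7%. So the check will run unless actual enrolment reaches at least 500.

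**2. Does OLS fail at this size?** The documents give no means, standard deviations or shares of zeros, so every distribution below is an assumption. Zero-inflated Poisson-lognormal counts were simulated with n = 300 or 340, 40% or 60% structural zeros, log-mean 1.5 and log-SD 1.0 or 1.3 among the active, and 1,500 replicates per scenario. Models adjusted for baseline value, state and gender. With no effect, rejection rates were:
- OLS: 3.5–4.9%
- log(1+y): 3.9–5.9%
- rank-based: 4.0–6.3%
- logistic, any versus none: 4.4–6.0%

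The primary test holds its level in these scenarios.

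**3. Can the alternatives answer another question?** Yes. This step used zero-inflated negative binomial counts, N = 400, 4,000 runs and no covariates; the control arm has mean 6, 50% structural zeros and dispersion 0.5. Rejection rates:

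| Scenario | OLS | log(1+y) | Mann-Whitney | Any vs none |
|---|---|---|---|---|
| Equal means, structural zeros 50% vs 60% | 5.1% | 14.8% | 23.5% | 32.6% |
| Means 6 vs 4, same structural zeros | 40.6% | 22.4% | 13.8% | 7.3% |

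With means 6 vs 4 and dispersion changed to 0.3 vs 0.8, the mean falls by 2.0 while mean log(1+y) rises by 0.08 and the share above zero rises by 9 points. The sign can reverse.

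**4. Does that make true positives look fragile?** It depends on the assumed effect.

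*40% fewer events among the active* (scenarios of step 2). Share of OLS-significant trials also significant by the other model:
- log(1+y): 64–81%
- rank-based: 35–60%
- logistic: 15–20%

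*25% fewer active participants.* OLS and rank verdicts differ in 30–50% of trials in the scenarios of step 2. A simpler run (n = 320, 50% zeros, baseline-adjusted, 1,500 replicates) shows the direction:
- OLS power was 14–23% and rank power 49–53%; verdicts differed in 34–39% of trials.
- Rank confirmed 84–93% of OLS-significant results, and log(1+y) 88–94%.
- OLS-only trials are therefore at most 23% × (1 − 0.84) = 3.7%. At least 34 − 3.7 = 30.3 points of the disagreement are rank finding an effect that OLS missed.

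*Partner-like counts* (log-mean 0.3–0.5, log-SD 0.5–0.6, 40–60% zeros). Under the 40% reduction, log(1+y) confirmed 80–89% of OLS-significant results and rank 58–78%. With 25% fewer active, the figures were 92–98% and 85–96%.

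**5. What would a check tied to β₁ add?** Re-randomisation inference for β₁ within assumed blocks in state-by-gender strata (700 replicates per scenario, 399 re-randomisations) confirmed 96–99% of OLS-significant results under the 40% reduction. It is nearly the same test, so it speaks to calibration, which step 2 already supports.

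**The case for a change.** The best case for a change is that it would be cheap and the choice is open late. Sensitivity analyses 1 to 3 refit the same model, whereas item 6 allows the estimated quantity to move while still calling itself a robustness test. The method is to be picked by unspecified diagnostics, although Appendix B says "the 9-month follow-up data collection began August 2017 and will end June 2020". Naming one method would need only wording and a short program.

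Part of this stands. The method is not named, footnote 40 lacks a binary outcome, and some permitted choices would not estimate β₁.

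The rest is weaker. The examples in item 6 are illustrative, and a non-parametric model need not be rank-based: a permutation or bootstrap analysis of the mean difference qualifies, and a Bayesian model can keep it too. The plan never says that a non-significant alternative makes the primary result fragile; footnote 40 speaks only of exploring differences. Disagreement may also come from noise, lower power or the pull of very large counts. That last cause matters because section 4)c.iii keeps outliers in the benchmark. A transformed or rank analysis is less sensitive to them, whereas re-randomising the same statistic is not designed to expose their influence. Restricting item 6 to β₁ would give up some of that information, although sensitivity analysis 4 recovers part by excluding outliers. On timing, no passage says that outcomes had been examined by arm.

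**Conclusion.** No change is needed. At 400 expected, item 6 will run with an unnamed method, and some choices would estimate something other than β₁. But the list's remark about an insufficient sample does not displace OLS: item 6 uses the alternative only for sensitivity analysis. The conclusion rests on the OLS test of β₁, which held 3.5–4.9% under the null at 300–340 analysed in the scenarios tried.

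The feared harm appears clearly only under one assumed effect, a uniform 40% drop among the active. Under the other effect tried, disagreement mostly runs the opposite way. All these rates rest on assumed distributions, so they illustrate what can happen and do not predict this trial.

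The unnamed method is a gap that analysts can fill sensibly by stating what each model estimates. The missing cut-point in footnote 40 is missing detail in an exploratory comparison. Confining item 6 to β₁ is a trade-off between a check on calibration and a check on the influence of large counts, and the plan's choice is defensible.

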Appendix A: Tables

Table 1. Behavioral outcomes used for primary impact analyses research questions

Outcome name	Description of the outcome, including how it is operationalized	Source of the measure	Timing of measure
Times having sex without condom	
The risk outcome is operationalized as the number of times in the past three months a person reports having any type of sex without using a condom.
 
The measure is calculated from the following items:
 
 • In the past 3 months, how many times have you had vaginal sex without using a condom? • In the past 3 months, how many times have you had oral sex without using a condom? • In the past 3 months, how many times have you had anal sex without using a condom? 
The measure is calculated by summing the total number of times a person reported not using a condom during vaginal, oral and anal sex.
 
The resulting variable is continuous with values that range from 0 to k, where 0 indicates that a person has not engaged in sex without a condom in the past three months, and k indicates the number of times the person has engaged in sex without a condom (risk behavior) in the past three months.
 
Note: the analytic sample will include all respondents who have nine-month follow-up data. Persons who indicate they have not had sex will be considered to have participated in the risk behavior 0 times (i.e., they did not engage in sex without a condom).
	Participant Questionnaire	Nine-month follow-up (nine months after the end of the 18-week intervention period)
Number of sexual partners	
The risk outcome is operationalized as the number of sexual partners in the past three months.
 
The measure is calculated from the following item:
 
 • How many sexual partners have you had in the past 3 months? 
The measure is calculated by summing the total number of sexual partners reported by the participant.
 
The resulting variable is continuous with values that range from 0 to k, where 0 indicates that a person has had no sexual partners in the past three months, and k indicates the number of sexual partners in the past three months.
	Participant Questionnaire	Nine-month follow-up (nine months after the end of the 18-week intervention period)

Note: the analytic sample will include all respondents who have nine-month follow-up data. Persons who indicate they have had no sexual contact will be considered to have 0 sexual partners.

Table 2. Covariates included in primary impact analyses

Covariate	Description of the covariate and how it will be used as a covariate in the analysis	Rationale for inclusion
Behavioral outcomes at baseline		
Times having sex without condoms	
The risk outcome is operationalized as the number of times in the past three months a person reports having any type of sex without using a condom.
 
The measure is calculated from the following items:
 
 • In the past 3 months, how many times have you had vaginal sex without using a condom? • In the past 3 months, how many times have you had oral sex without using a condom? • In the past 3 months, how many times have you had anal sex without using a condom? 
The measure is calculated by summing the total number of times a person reported not using a condom during vaginal, oral and anal sex.
 
The resulting variable is continuous with values that range from 0 to k, where 0 indicates that a person has not engaged in sex without a condom in the past three months, and k indicates the number of times the person has engaged in sex without a condom (risk behavior) in the past three months.
	Times having sex without condoms is included in the primary impact analysis as the pre-intervention or baseline measure of the behavioral outcome; it is included in the models so that individual-level change or difference can be assessed at the nine-month follow-up.
Individual level covariates		
Age	
The variable is measured as the respondent's age in years at screening.
 
The measure is constructed from the following item on the recruitment and eligibility form:
	Research has shown that likelihood of engaging in sex increases with age, while use of condoms declines and number of sexual partners increases

Covariate	Description of the covariate and how it will be used as a covariate in the analysis	Rationale for inclusion
	
 • Date of birth 
The variable is calculated by subtracting the reported date of birth given from the date when the screening was completed.
 
The resulting variable is continuous with values ranging from 14 to 19.
	(brewster 1999; kirby 2007; miller et al 1998; scott-jones and white 1990)
Race	
The measure is operationalized a set of $n-1$ dummy variables, where n refers to the categorized race.
 
The measure is taken from the following item on the baseline Participant Questionnaire:
 
 • What is your race? (Participants can select more than one response) 
 ○ White ○ Black or African American ○ Hispanic, Latino, or of Spanish origin ○ American Indian or Alaska Native ○ Asian ○ Native Hawaiian or Pacific Islander ○ Some other race (specify) 
The category Hispanic, Latino, or of Spanish Origin is not considered in the operationalization of the race variable (it is used to create a separate Hispanic/Latino indicator variable). Remaining responses are recoded into the following mutually exclusive categories and dummy variables are created for each: White only, Black only, Other race only (which includes American Indian/Alaskan Native, Asian, Native Hawaiian/Other Pacific Islander, and Other), Race not selected (individual did not select any racial category), and Multiracial (which includes individuals who selected more than one racial category).
 
Each dummy will be coded as 1 if the individual is coded as that particular race and 0 otherwise.
	Research has shown that Black/African American and Hispanic adolescents are more likely to engage in sex during adolescence and initiate sexual activity at a younger age (Blum 2000; Brewster 1999; Hogan et al 2000; Kirby 2007; Scott Jones and White 1990)

Covariate	Description of the covariate and how it will be used as a covariate in the analysis	Rationale for inclusion
Hispanic, Latino or of Spanish origin	
The measure is operationalized as a dummy variable, where 0 = identify as another ethnicity/do not identify ethnicity; 1 = identify as Hispanic, Latino or of Spanish origin.
 
The measure is taken from the following item on the baseline Participant Questionnaire:
 
 • What is your race? (Participants can select more than one response) 
  White  Black or African American  Hispanic, Latino, or of Spanish origin  American Indian or Alaska Native  Asian  Native Hawaiian or Pacific Islander  Some other race (specify) 	
Research has shown that Black/African American and Hispanic adolescents are more likely to engage in sex during adolescence and initiate sexual activity at a younger age (Blum 2000; Brewster 1999; Hogan et al 2000; Kirby 2007; Scott Jones and White 1990)

Covariate	Description of the covariate and how it will be used as a covariate in the analysis	Rationale for inclusion
High school education	
This measure is operationalized as a dummy variable, where individuals with a high school education are coded as 1 and all others are coded as 0.
 
The measure is taken directly from the following item on the baseline participant questionnaire:
	
Blocking covariates		
State	
The measure is operationalized a set of $n-1$ dummy variables, where n refers to the number of the states over the course of the evaluation period.
	Randomization is blocked by state.
	
Data for the measure are obtained from the enrollment log database.
	
	
Each dummy will be coded as 1 if the individual is enrolled in a particular state and 0 otherwise. State 1 is the reference variable. Dummy variables will be grand mean centered so that the intercept will then reflect the un-weighted mean site effect.
	
Gender	
The measure is operationalized as a dichotomous variable, where 1 indicates that the participant enrolled is female and 0 if otherwise.
	Randomization is blocked by gender.
	
Data for the measure are obtained from the enrollment log database.
	

Table 3: Data Editing Rules

The following table provides PRG's general rules for editing data based upon responses given.

Category	Data editing rule
No response given to an item (coded as .f)	If data from a related variable can be used to infer a value, data will be logically edited. Otherwise, the value will be left as missing.
Invalid items (coded as .i)	Adjust missing baseline values
Outlying items (Outlier indicator variable coded as 1)	Keep in benchmark analysis; run sensitivity analyses excluding outliers
Inconsistent across-time items (coded as .k)	Adjust missing baseline values
Unreliable cases (Unreliable indicator variable codes as 1)	Exclude case from benchmark analysis; run sensitivity analyses including unreliable cases

